7.2. Secondary Efficacy Analysis

The following secondary endpoints will be assessed using the FAS:

- WOMAC LK3.1 OA Index (pain) – change in pain score between Baseline and Week 1

and 2.

- *WOMAC LK3.1 OA Index (stiffness)* between Baseline and Week 1, Week 2, and Week 4.
- *WOMAC LK3.1 OA Index (physical function)* between Baseline and Week 1, Week 2, and Week 4.
- *WOMAC LK3.1 OA Index (composite score)* between Baseline and Week 1, Week 2, and Week 4.
- *Patient Global Assessment (PGA)* between Baseline and Week 4.
- *Patient Global Impression (PGI) of Change* between Week 1 and Week 4.
- *Pain intensity assessed on an 11-point numeric rating scale (NRS)* between Baseline and Week 1, Week 2, and Week 4.
- *Use of rescue medication* between Baseline and Week 1, Week 2, and Week 4.

All WOMAC LK3.1 OA Indices, PGA, PGI, and NRS secondary efficacy analyses will be performed similar to the primary analyses. An MMRM model will be used with change from baseline as the repeated dependent variable, with treatment (HP-5000-[REDACTED], HP-5000-[REDACTED], and placebo), visit, treatment-by-visit interaction, and the baseline assessment score as covariates.

The observed value and change from baseline each assessment score will also be summarized descriptively by visit using summary statistics in addition to the above noted model.

Figures of the Least Squared Means (LSM) of change from baseline will be plotted by treatment group and overall for the FAS for all by-visit outcomes. Within these figures, treatments will be distinguished by color and line type and jittered to prevent over-plotting at each visit. Each LS mean will include whiskers within a 95% confidence interval around the plotted value.

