7.2.1. Responder Based on $\geq X\%$ Improvement¹¹ from Baseline

At each time point, subjects having X% or greater improvement from baseline in WOMAC pain score will be defined as “responders”. The percentage change will be defined as (Value at Week X – Baseline value) * 100 / (Baseline value). In other words, the responder indicator will be set to 1 if the percentage change is less than or equal to -X% and set to 0 if the percentage change is greater than -X% or missing. The different levels of required percent improvement from baseline are X=5% to 100% with 5% increments. These different thresholds for improvement will be summarized by visit for the FAS. Results will be reported by means of a graph with response threshold on the X-axis and proportion of responders in each treatment group on the Y-axis, this figure will only be completed for WOMAC pain. Corresponding data will be presented in a summary table. WOMAC stiffness, physical function, composite score, and NRS Pain improvement will be analysed similarly in separate tables.

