13.1. Planned Table Descriptions

The following are planned summary tables for protocol number HP-5000-US-05. The table numbers and page numbers are place holders only and will be determined when the tables are produced.

Please note, the following six tables will be generated as top-line deliverables:

1. Tables 14.1.1 “Study Population and Subject Disposition”, All Enrolled Subjects;
2. Table 14.2.1.2.2 “MMRM Analysis of WOMAC Pain Score by Study Visit”, FAS;
3. Table 14.2.2.2 “MMRM Analysis of WOMAC Stiffness Score by Study Visit”, FAS;
4. Table 14.2.3.2 “MMRM Analysis of WOMAC Physical Function Score by Study Visit”, FAS;
5. Table 14.2.7.2 “MMRM Analysis of Pain Intensity Assessed on an 11-Point Numeric Rating Scale (NRS) by Study Visit”, FAS;
6. Table 14.3.4.1.1 “Dermal Safety for Adhesion Assessment by Study Visit”, SAF

Table Number	Population	Table Title

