[1] Estimates are from a repeated measures mixed model with change from baseline as the dependent variable and subject as the random repeated factor. Terms for treatment, visit, treatment-by-visit, and baseline WOMAC Pain Score as covariates are included. The Kenward Roger approximation for denominator degrees of freedom is implemented and the restricted maximum likelihood (REML) approach for estimation is used. An unstructured covariance matrix converged.

SOURCE: Listings xx.x.x, xx.x.x

T:\Noven\HP-5000-US-05\...\xxxxxx.sas run on DDMMYY at HH:MM for data extracted on DDMMYY, on SAS v9.4

{Programming Note: If type=un fails to converge, follow SAP guidance and update footnote indicating which covariance structure is used.
 Repeat above layout for Week 2, and Week 4, and also repeat for Non-Target Knee }

Statistical Analysis Plan,
 Sponsor Noven Pharmaceuticals, Inc.
 Protocol Number HP-5000-US-05
 [REDACTED]

Noven Pharmaceuticals, Inc.
 Protocol HP-5000-US-05

Page 1 of x
 FINAL

Table 14.2.7.3
 Responder Analysis of Pain Intensity Assessed on an 11-Point Numeric Rating Scale (NRS) by Study Visit
 Full Analysis Set

Parameter	HP-5000-[REDACTED] (N=xx) n (%)	HP-5000-[REDACTED] (N=xx) n (%)	Overall HP-5000 (N=xx) n (%)	Placebo (N=xx) n (%)
Target Knee				
Week 1				
n	xx	xx	xx	xx
5% Improvement				
Responder	xx (xx.x%)	xx (xx.x%)	xx (xx.x%)	xx (xx.x%)
Non-Responder	xx (xx.x%)	xx (xx.x%)	xx (xx.x%)	xx (xx.x%)
10% Improvement				
Responder	xx (xx.x%)	xx (xx.x%)	xx (xx.x%)	xx (xx.x%)
Non-Responder	xx (xx.x%)	xx (xx.x%)	xx (xx.x%)	xx (xx.x%)
15% Improvement				
Responder	xx (xx.x%)	xx (xx.x%)	xx (xx.x%)	xx (xx.x%)
Non-Responder	xx (xx.x%)	xx (xx.x%)	xx (xx.x%)	xx (xx.x%)

Note: Percentages are (n/N)*100, where N is the number of non-missing subjects at a given study visit. WOMAC = West Ontario and McMasters Universities Osteoarthritis Index.

Treatment arms: HP-5000-[REDACTED] topical patch, HP-5000-[REDACTED] topical patch, and Placebo.

[1] At each time point, subjects having a x% or greater improvement from baseline in WOMAC pain score will be defined as a "Responder", where x% ranges from 5% to 100%.

SOURCE: Listings xx.x.x, xx.x.x

T:\Noven\HP-5000-US-05\...\xxxxxx.sas run on DDMMYY at HH:MM for data extracted on DDMMYY, on SAS v9.4

{Programming Note: Repeat above layout %'s from 5% to 100% for Responders and for Week 2, and Week 4}

Statistical Analysis Plan,
 Sponsor Noven Pharmaceuticals, Inc.
 Protocol Number HP-5000-US-05
 [REDACTED]

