Note: WOMAC = West Ontario and McMasters Universities Osteoarthritis Index. Treatment arms: HP-5000- [REDACTED] topical patch, HP-5000- [REDACTED] topical patch, and Placebo.

[1] Range from 0 to 20 by summing each item relating to Pain.

[2] Range from 0 to 8 by summing each item relating to Stiffness.

[3] Range from 0 to 68 by summing each item relating to Physical Function.

[4] Calculated by summing the items for all 3 subscales (Pain, Stiffness, and Physical Function) and then dividing by 96. Higher scores on the WOMAC indicate worse pain, stiffness, and functional limitations.

T:\Noven\HP-5000-US-05\...\xxxxxx.sas run on DDMMYY at HH:MM for data extracted on DDMMYY, on SAS v9.4

Statistical Analysis Plan,
 Sponsor Noven Pharmaceuticals, Inc.
 Protocol Number HP-5000-US-05
 [REDACTED]

Noven Pharmaceuticals, Inc.
 Protocol HP-5000-US-05

Page 1 of x
 FINAL

Listing 16.2.6.2
 Patient Global Assessment (PGA)
 Full Analysis Set

Actual Treatment: XXXXXXX

Subject ID	Visit	Assessment Date	How would you rate your osteoarthritis condition over the last 24 hours?
XXXXX	Baseline	DDMMYY	XXXXXXXXXXXXXXXXXXXXXXXXXX
	Week 1	DDMMYY	XXXXXX
	Week 2	DDMMYY	XXXXXXXXXXXXXXXXXXXX
	Week 4	DDMMYY	XXXXXXXXXXXX
XXXXX	Baseline	DDMMYY	XXXXXXXXXXXXXX
	Week 1	DDMMYY	XXXXXX
	Week 2	DDMMYY	XXXXXXXXXXXXXXXXXXXXXX
	Week 4	DDMMYY	XXXXXXXXXXXXXXXXXXXXXX

Note: PGA is a 1 to 7 scale where 1 = "Very Much Improved", 2 = "Much Improved", 3 = "Minimally Improved", 4 = "No Change", 5 = "Minimally Worse", 6 = "Much Worse", and 7 = "Very Much Worse". Treatment arms: HP-5000- [REDACTED] topical patch, HP-5000- [REDACTED] topical patch, and Placebo.

T:\Noven\HP-5000-US-05\...\xxxxxx.sas run on DDMMYY at HH:MM for data extracted on DDMMYY, on SAS v9.4

Statistical Analysis Plan,
 Sponsor Noven Pharmaceuticals, Inc.
 Protocol Number HP-5000-US-05
 [REDACTED]

Noven Pharmaceuticals, Inc.
 Protocol HP-5000-US-05

Page 1 of x
 FINAL

Listing 16.2.6.3
 Patient Global Impression (PGI) of Change
 Full Analysis Set

Actual Treatment: XXXXXXX

Subject ID	Visit	Assessment Date	How would you rate your overall improvement with treatment during the clinical trial?
XXXXX	Week 1	DDMMYY	XXXXXXXX
	Week 2	DDMMYY	XXXXXXXXXXXXXXXXXXXX
	Week 4	DDMMYY	XXXXXXXXXXXX
XXXXX	Week 1	DDMMYY	XXXXXXXXXXXX
	Week 2	DDMMYY	XXXXXXXXXXXXXXXXXXXX
	Week 4	DDMMYY	XXXXXXXXXXXXXXXX

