Note: PGI is a 0 to 4 scale where 0 = "Very Good", 1 = "Good", 2 = "Moderate", 3 = "Poor", and 4 = "Very Poor". Treatment arms: HP-5000-[REDACTED] topical patch,
 HP-5000-[REDACTED] topical patch, and Placebo.

T:\Noven\HP-5000-US-05\...\xxxxxx.sas run on DDMMYY at HH:MM for data extracted on DDMMYY, on SAS v9.4

Statistical Analysis Plan,
 Sponsor Noven Pharmaceuticals, Inc.
 Protocol Number HP-5000-US-05
 [REDACTED]

Noven Pharmaceuticals, Inc.
 Protocol HP-5000-US-05

Page 1 of x
 FINAL

Listing 16.2.6.4
Pain Intensity Assessed on an 11-Point Numeric Rating Scale (NRS)
Full Analysis Set

Actual Treatment: XXXXXXX

Subject ID	Visit	Assessment Date	Worst NRS Pain		Worst NRS Pain Score [2]	Overall NRS Pain (Target Knee)	Overall NRS Pain (Non-Target Knee)	Average NRS Pain Score [1]
			(Target Knee)	(Non-Target Knee)				
XXXXX	Diary	DDMMYY	xx	xx		xx	xx	
	Diary	DDMMYY	xx	xx		xx	xx	
	Diary	DDMMYY	xx	xx		xx	xx	
	Baseline	DDMMYY	xx	xx	xx	xx	xx	xx
	Diary	DDMMYY	xx	xx		xx	xx	
	Diary	DDMMYY	xx	xx		xx	xx	
	Diary	DDMMYY	xx	xx		xx	xx	
	Diary	DDMMYY	xx	xx		xx	xx	
	Diary	DDMMYY	xx	xx		xx	xx	
	Week 1	DDMMYY	xx	xx	xx	xx	xx	xx

Note: NRS is an 11-point scale from 0 to 10 where 0 = no pain and 10 = the worst pain imaginable, a value in the middle, around 5 would be moderate pain; a value of 2 or 3 would be mild pain and value of 7 or higher is considered severe pain. Treatment arms: HP-5000-[REDACTED] topical patch, HP-5000-[REDACTED] topical patch, and Placebo.

[1] Average of NRS pain scores reported for pain over the last 24 hours for the last 3 days prior to each clinic or phone visit.

[2] Worst NRS pain score reported for pain over the last 24 hours for the last 3 days prior to each clinic or phone visit

T:\Noven\HP-5000-US-05\...\xxxxxx.sas run on DDMMYY at HH:MM for data extracted on DDMMYY, on SAS v9.4

Statistical Analysis Plan,
 Sponsor Noven Pharmaceuticals, Inc.
 Protocol Number HP-5000-US-05
 [REDACTED]

Noven Pharmaceuticals, Inc.
 Protocol HP-5000-US-05

Page 1 of x
 FINAL

Listing 16.2.6.5
 Rescue Medication Use
 Full Analysis Set

Actual Treatment: XXXXXXX

Subject ID	Visit (Study Day)	Rescue medication dispensed?	Medication Name/ Bottle No./ Date Dispensed	Dispensed Amount (units)	Date Dispensed/ Date Returned	Returned Amount (units)	Lose Dose YN?	Reason
XXXXX	Baseline (xx)	No						
	Week 1 (xx)	No						
	Week 2 (xx)	Yes	xxxxxxxxxxxxxxxxxxxxxx xxxxxxxx/ xxxxx	xxxx (xxx)	DDMMYYYY/ DDMMYYYY	xxxx (xxx)	No	

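### SAP output shells for secondary endpoints contradict the SAP text: the NRS model and NRS responder footnotes name WOMAC pain, and the PGA and PGIC listing keys are swapped

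*SAP*

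**What the plan says.** **Model covariate.** SAP 7.2 covers the WOMAC indices, PGA, PGI and NRS. It specifies a mixed model for change from baseline with treatment, "visit, treatment-by-visit interaction, and the baseline assessment score as covariates". The shell for Table 14.2.7.2 is the NRS version of that model. SAP 13.1 lists it among the six top-line deliverables as "MMRM Analysis of Pain Intensity Assessed on an 11-Point Numeric Rating Scale (NRS) by Study Visit". Its footnote [1] reads: "Terms for treatment, visit, treatment-by-visit, and baseline WOMAC Pain Score as covariates are included".

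The mixed-model shells for WOMAC stiffness (14.2.2.2), physical function (14.2.3.2), composite (14.2.4.2) and PGA (14.2.5.2) are not written out. Each says to repeat Table 14.2.1.2.3, and the footnote of that table also names baseline WOMAC pain.

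**NRS responders.** SAP 7.2.1 defines responders for WOMAC pain and then states: "WOMAC stiffness, physical function, composite score, and NRS Pain improvement will be analysed similarly in separate tables". The footnote of the NRS responder shell, Table 14.2.7.3, says that "subjects having a x% or greater improvement from baseline in WOMAC pain score will be defined as a" responder.

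**Listing keys.** The note to Listing 16.2.6.2 (PGA) begins "PGA is a 1 to 7 scale where 1" and gives the seven change categories. The note to Listing 16.2.6.3 (PGIC) begins "PGI is a 0 to 4 scale where 0" and gives the five status categories. Protocol 10.2.1.2 and 10.2.1.3 define the scales the other way round: PGA runs 0 to 4 and PGIC runs 1 to 7.

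**The concern.** Programmers work from shells, and these are marked as final. Where shell and text disagree, someone has to choose between them, and that choice would be made outside the pre-specified plan.

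For the NRS model, the shell takes away the covariate that explains most about the NRS outcome and puts in another instrument's baseline. That would lower precision and leave part of any chance imbalance in baseline NRS in the estimate, in a table released at top line. If the repeat instructions are taken literally, stiffness and physical function have the same fault. Three of the six top-line tables would then carry a covariate that SAP 7.2 does not specify.

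For Table 14.2.7.3, following the footnote would print WOMAC pain responders under an NRS title. The table would duplicate Table 14.2.1.7, and the NRS responder result would be missing.

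The listing keys affect only how a listing is read. Under the printed keys a PGIC code of 4 (No Change) reads as Very Poor, PGIC codes 5 to 7 have no label, and a PGA code of 0 has no label.

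**Working it through.** **Text against shell**

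| Output | SAP text or protocol | Shell |
|---|---|---|
| 14.2.7.2, NRS model (top-line) | baseline of the assessment analysed (SAP 7.2) | baseline WOMAC pain |
| 14.2.2.2 stiffness and 14.2.3.2 function (both top-line), 14.2.4.2 composite, 14.2.5.2 PGA | same (SAP 7.2) | repeat 14.2.1.2.3, whose footnote names baseline WOMAC pain |
| 14.2.6.2, PGIC model | instrument has no baseline | explicit instruction to remove the covariate |
| 14.2.7.3, NRS responders | NRS pain improvement (SAP 7.2.1) | WOMAC pain improvement |
| 14.2.5.3, PGA responders | Very Good or Good (SAP 7.2.3) | Very Good or Good, with PGA baseline |
| 14.2.6.3, PGIC responders | Very Much or Much Improved (SAP 7.2.2) | agrees |
| Listing 16.2.6.2, PGA key | 0 to 4 (Protocol 10.2.1.2) | 1 to 7 |
| Listing 16.2.6.3, PGIC key | 1 to 7 (Protocol 10.2.1.3) | 0 to 4 |

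The PGIC row shows that the authors wrote down a covariate change when they wanted one. The four repeated shells have no such note.

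**Size of the covariate effect**

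The plan states no figure to reproduce. This is an illustration at a single visit; the planned model also uses the other visits. Every input is an assumption, because the documents give no correlations or SDs for these scores.

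- Follow-up NRS, Y, has SD 1. Baseline NRS, B, has SD k, with k = 1, 0.75 or 0.5. Smaller k stands for a baseline range narrowed by the pain entry threshold.
- ρ = corr(B, Y), taken as 0.3 to 0.6.
- r = corr(B, W), where W is baseline WOMAC pain, taken as 0.3 to 0.7.
- W is related to Y only through B.

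Residual variance of the change Y − B:

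- adjusted for B: 1 − ρ²
- adjusted for W: 1 + k² − 2kρ − [r(ρ − k)]²

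k = 1:
- ρ = 0.3, r = 0.3: (2 − 0.6 − 0.0441) / 0.91 = 1.3559 / 0.91 = 1.49
- ρ = 0.6, r = 0.7: (2 − 1.2 − 0.0784) / 0.64 = 0.7216 / 0.64 = 1.13

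k = 0.75:
- ρ = 0.3, r = 0.3: (1.5625 − 0.45 − 0.0182) / 0.91 = 1.0943 / 0.91 = 1.20
- ρ = 0.6, r = 0.7: (1.5625 − 0.9 − 0.0110) / 0.64 = 0.6515 / 0.64 = 1.02

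k = 0.5:
- ρ = 0.3, r = 0.3: (1.25 − 0.3 − 0.0036) / 0.91 = 0.9464 / 0.91 = 1.04
- ρ = 0.5, any r: (1.25 − 0.5 − 0) / 0.75 = 1.00

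The SE ratio is the square root of the variance ratio:

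| Baseline SD / follow-up SD | Variance increase | SE increase |
|---|---|---|
| 1 | 13-49% | 6-22% |
| 0.75 | 2-20% | 1-10% |
| 0.5 | 0-4% | 0-2% |

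**PGA responder classes.** Applying the SAP 7.2.3 and Table 14.2.5.3 rule to the 0 to 4 scale makes Very Good and Good responders, and Moderate, Poor and Very Poor non-responders. That is what was intended. No responder table takes its classes from the listing keys.

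**The case against.** The strongest reply is that the governing text and code already point to the right model. SAP 7.2 asks for the assessment's own baseline. The example code in SAP 7.1 uses a generic baseline variable, which on NRS records would be the NRS baseline. The footnote looks like template carry-over, since the abbreviation note of the same shell expands WOMAC but not NRS. Table 14.2.7.3 likewise has an NRS title and a target-knee row. On this view the likely result is a mislabelled footnote on a correct analysis. That is fair, and it makes the harm conditional on the shell being followed. It does not remove the contradiction, because Table 14.2.7.2 was written out in full and states its covariate explicitly.

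It is also fair that the size rests entirely on assumed values. NRS pain is an entry criterion, so a narrowed baseline range, and with it the small end of the table, is plausible.

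Two stronger readings are tempting, and the documents support neither.

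- A reader might infer that the PGA responder classes would be wrong. SAP 7.2.3 and Table 14.2.5.3 both give the response labels and agree, and the swapped keys sit only in listing notes. Protocol 18.2 does number the answers 1 to 5, but it calls itself a sample, states 0 to 4 just above that list, and defers to the study reference manual for the actual form. Misclassification would need a database coded 1 to 5 and a programmer who ignored the labels, and nothing in the documents shows either.
- A reader might infer that the wrong covariate biases the NRS comparison. The arms are randomised, so it costs precision and leaves chance imbalance in the estimate, without a systematic shift.

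**Conclusion.** The point stands as a contradiction between SAP text and SAP shells for secondary endpoints, and it should be corrected. Two stated shell rules would give the wrong output if followed: the NRS model covariate and the NRS responder definition. Four further model shells inherit the wrong covariate by reference, and two listing keys are exchanged. The primary analysis is not affected, because baseline WOMAC pain is its proper covariate.

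The textual conflict is certain; the size is not. Over the assumed ranges the SE of the NRS difference could be up to about 22% larger or practically unchanged, depending mainly on how far the baseline SD falls below the follow-up SD. The NRS responder table needs no such assumption: read literally, it reports a different endpoint from its title. The listing swap is a labelling error with no inferential effect.

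**What to change.** Amend the SAP shells before unblinding:

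1. Table 14.2.7.2, footnote [1]: replace baseline WOMAC Pain Score with baseline NRS score.
2. Tables 14.2.2.2, 14.2.3.2, 14.2.4.2 and 14.2.5.2: add to each repeat instruction that the covariate is the baseline of the instrument in that table.
3. Table 14.2.7.3, footnote [1]: define a responder as x% or greater improvement from baseline in the NRS pain score.
4. Listings 16.2.6.2 and 16.2.6.3: exchange the two scale keys, so that PGA shows 0 to 4 and PGIC shows 1 to 7.

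No change to SAP 7.2.3 or Protocol 18.2 is needed for this point. The cost is two table footnotes, four programming notes and two listing notes. It needs no new data, no protocol amendment and no change to the primary analysis.

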8.1. Adverse Events

All adverse events collected are treatment-emergent adverse events (TEAEs) since only AEs after treatment start are collected. All AEs, and SAEs will be coded using the MedDRA version 19.0 thesaurus.

The frequency and percentage of subjects reporting AEs, grouped by MedDRA system organ class and preferred term, will be tabulated by severity and treatment group for the SAF. Such summaries will be displayed for AEs, SAEs, AEs by relationship to study drug, and AEs by severity.

In the case of multiple occurrences of the same AE within the same subject, each subject will only be counted once for each preferred term. In the summaries showing severity and relationship to study medication the event with the maximum severity or strongest relationship will be reported. If a particular event is missing the severity and/or relationship, then the strongest possible severity or relationship will be assumed for analysis (severity = severe, relationship = definitely related).

Missing and partially missing AE start and/or stop dates will be imputed for the purpose of statistical analysis, according to the specifications described in Section [5.1.8](#).

In the AE data listings, all AEs will be displayed.

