14.3 Safety And Tolerability Tables

14.3.1 Displays Of Adverse Events

14.3.1.1	SAF	Summary of all Adverse Events
14.3.1.2	SAF	Summary of Adverse Events by System Organ Class and Preferred Term
14.3.1.3	SAF	Summary of Adverse Events by Severity and Relationship to Study Medication, System Organ Class and Preferred Term
14.3.1.4	SAF	Adverse Events Leading to Premature Withdrawal from the Study by System Organ Class and Preferred Term
14.3.1.5	SAF	Summary of Serious Adverse Events by System Organ Class and Preferred Term
14.3.1.6	SAF	Adverse Events Leading to Death by System Organ Class and Preferred Term

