Note: Treatment arms: HP-5000-[REDACTED] topical patch, HP-5000-[REDACTED] topical patch, and Placebo.

SOURCE: Listings xx.x.x, xx.x.x

T:\Noven\HP-5000-US-05\...\xxxxxx.sas run on DDMMYYYY at HH:MM for data extracted on DDMMYYYY, on SAS v9.4

Statistical Analysis Plan,
 Sponsor Noven Pharmaceuticals, Inc.
 Protocol Number HP-5000-US-05
 [REDACTED]

Noven Pharmaceuticals, Inc.
 Protocol HP-5000-US-05

Page 1 of 1
 FINAL

Table 14.3.1.1
 Summary of all Adverse Events
 Safety Analysis Set

Category	HP-5000-[REDACTED] (N=xx) n (%)	HP-5000-[REDACTED] (N=xx) n (%)	Overall HP-5000 (N=xx) n (%)	Placebo (N=xx) n (%)
Subjects with at Least One Adverse Event	xx (xx.x%)	xx (xx.x%)	xx (xx.x%)	xx (xx.x%)
Adverse Event Potentially Related to Study Drug [1]	xx (xx.x%)	xx (xx.x%)	xx (xx.x%)	xx (xx.x%)
Serious Adverse Event	xx (xx.x%)	xx (xx.x%)	xx (xx.x%)	xx (xx.x%)
Serious Adverse Event Potentially Related to Study Drug [1]	xx (xx.x%)	xx (xx.x%)	xx (xx.x%)	xx (xx.x%)
Adverse Event Leading to Study Drug Withdrawal	xx (xx.x%)	xx (xx.x%)	xx (xx.x%)	xx (xx.x%)
Adverse Event Leading to Death	xx (xx.x%)	xx (xx.x%)	xx (xx.x%)	xx (xx.x%)

Note: Percentages are (n/N)*100. Treatment groups are based on treatment received. All adverse events collected are treatment-emergent adverse events (TEAEs) since only AEs after treatment start are collected. Treatment arms: HP-5000-[REDACTED] topical patch, HP-5000-[REDACTED] topical patch, and Placebo.

[1] Any AE determined as "Possibly Related" or "Definitely Related" are considered as potentially related to study drug.

SOURCE: Listings xx.x.x, xx.x.x

T:\Noven\HP-5000-US-05\...\xxxxxx.sas run on DDMMYY at HH:MM for data extracted on DDMMYY, on SAS v9.4

Statistical Analysis Plan,
 Sponsor Noven Pharmaceuticals, Inc.
 Protocol Number HP-5000-US-05
 [REDACTED]

Noven Pharmaceuticals, Inc.
 Protocol HP-5000-US-05

Page 1 of x
 FINAL

Table 14.3.1.2
 Summary of Adverse Events by System Organ Class and Preferred Term
 Safety Analysis Set

System Organ Class Preferred Term	HP-5000-[REDACTED] (N=xx)		HP-5000-[REDACTED] (N=xx)		Overall HP-5000 (N=xx)		Placebo (N=xx)	
	Events n	Subjects n(%)	Events n	Subjects n(%)	Events n	Subjects n(%)	Events n	Subjects n(%)
Number of Subjects with at Least One AE	xx	xx (xx.x%)	xx	xx (xx.x%)	xx	xx (xx.x%)	xx	xx (xx.x%)
SOC 1	xx	xx (xx.x%)	xx	xx (xx.x%)	xx	xx (xx.x%)	xx	xx (xx.x%)
PT 1	xx	xx (xx.x%)	xx	xx (xx.x%)	xx	xx (xx.x%)	xx	xx (xx.x%)
PT 2	xx	xx (xx.x%)	xx	xx (xx.x%)	xx	xx (xx.x%)	xx	xx (xx.x%)

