Note: Percentages are (n/N)*100. Treatment groups are based on treatment received. Subjects were counted only once for each System Organ Class and Preferred Term. A subject with multiple events per System Organ Class or per Preferred Term is counted only once at maximum reported severity. For the Events column, multiple events for a subject that are in the same AE category are counted multiple times in that AE category. All adverse events collected are treatment-emergent adverse events (TEAEs) since only AEs after treatment start are collected. Treatment arms: HP-5000 [REDACTED] topical patch, HP-5000 [REDACTED] topical patch, and Placebo.

[1] Adverse events were coded using MedDRA version 19.0.

SOURCE: Listings xx.x.x, xx.x.x

T:\Noven\HP-5000-US-05\...\xxxxxx.sas run on DDMMYYYY at HH:MM for data extracted on DDMMYYYY, on SAS v9.4

{Programming Note: Sort alphabetically for SOC and decreasing frequency for PT of overall, continue for all combinations of severity and relationship. Do not show 0 count rows}

Statistical Analysis Plan,
Sponsor Noven Pharmaceuticals, Inc.
Protocol Number HP-5000-US-05
[REDACTED]

Table 14.3.1.4
Adverse Events Leading to Premature Withdrawal from the Study by System Organ Class and Preferred Term
Safety Analysis Set

{Programming Note: Repeat table 14.3.1.2}

Table 14.3.1.5
Summary of Serious Adverse Events by System Organ Class and Preferred Term
Safety Analysis Set

{Programming Note: Repeat table 14.3.1.2}

Table 14.3.1.6
Adverse Events Leading to Death by System Organ Class and Preferred Term
Safety Analysis Set

{Programming Note: Repeat table 14.3.1.2}

Statistical Analysis Plan,
 Sponsor Noven Pharmaceuticals, Inc.
 Protocol Number HP-5000-US-05
 [REDACTED]

Noven Pharmaceuticals, Inc.
 Protocol HP-5000-US-05

Page 1 of x
 FINAL

Table 14.3.2.1.1
 Summary of Change from Baseline for Clinical Chemistry parameters at Week 4
 Safety Analysis Set

Analyte	HP-5000-[REDACTED] (N=xx)	HP-5000-[REDACTED] (N=xx)	Overall HP-5000 (N=xx)	Placebo (N=xx)
Visit Statistics				
Analyte (unit)				
Baseline				
n	xx	xx	xx	xx
Mean (95% CI)	xx.xx (x.xx, x.xx)	xx.xx (x.xx, x.xx)	xx.xx (x.xx, x.xx)	xx.xx (x.xx, x.xx)
Standard Deviation	xx.XXX	xx.XXX	xx.XXX	xx.XXX
Median	xx.xx	xx.xx	xx.xx	xx.xx
Minimum, Maximum	xx.X, xx.X	xx.X, xx.X	xx.X, xx.X	xx.X, xx.X
Week 4				
n	xx	xx	xx	xx
Mean (95% CI)	xx.xx (x.xx, x.xx)	xx.xx (x.xx, x.xx)	xx.xx (x.xx, x.xx)	xx.xx (x.xx, x.xx)
Standard Deviation	xx.XXX	xx.XXX	xx.XXX	xx.XXX

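### Table 14.3.1.3 places each subject at maximum severity only, so subject counts of drug-related adverse events by preferred term can be understated and cannot be recovered from any planned summary table

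*SAP*

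**What the plan says.** SAP 8.1 (Adverse Events) treats relationship and severity as separate summaries: "Such summaries will be displayed for AEs, SAEs, AEs by relationship to study drug, and AEs by severity". For a subject with repeated events it gives a two-part rule: "In the summaries showing severity and relationship to study medication the event with the maximum severity or strongest relationship will be reported". Protocol 13.4.4.1 also requires adverse events to be summarised by severity and by relationship.

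The planned table list (SAP 13.1, under 14.3.1) has six adverse event tables. Only Table 14.3.1.3 shows relationship by preferred term. Its title is "Summary of Adverse Events by Severity and Relationship to Study Medication, System Organ Class and Preferred Term".

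The shell in SAP 14.2 lists the preferred term, then severity, then the four relationship grades under each severity, and the programmer is told to "continue for all combinations of severity and relationship". Every row has an Events column and a Subjects n (%) column. The footnote gives each column its own rule:

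- Subjects: "A subject with multiple events per System Organ Class or per Preferred Term is counted only once at maximum reported severity".
- Events: "For the Events column, multiple events for a subject that are in the same AE category are counted multiple times in that AE category".

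The footnote has no rule for choosing among relationship grades.

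**The concern.** The table puts two questions through one counting rule. Maximum severity is the right rule for asking how many subjects had a severe event of a term. It is the wrong rule for asking how many subjects had an event of that term attributed to the patch, because the most severe event need not be the one the investigator attributed to study drug. For the second question, SAP 8.1 already names the appropriate rule, strongest relationship, but the shell does not carry it out.

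At stake is a routine safety output: the incidence of drug-related events by term and arm. Safety and tolerability is a stated secondary objective, and the two active formulations will be compared on such counts when one is considered for further development.

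**Working it through.** The plan states no figure to reproduce, so the check applies the footnote's rules to possible data.

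**Inputs.** Three severity grades (mild, moderate, severe) and four relationship grades (not, unlikely, possibly, definitely), from the Table 14.3.1.3 shell. Related means possibly or definitely, as SAP 5.1.7 and the Table 14.3.1.1 footnote define it.

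**One subject, one preferred term, two events.** Event A is mild and definitely related. Event B is severe and not related.

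| Row | Events | Subjects |
|---|---|---|
| Mild / Definitely Related | 1 | 0 |
| Severe / Not Related | 1 | 1 |

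The related event is visible as an event. The subject is in no related row. Under the strongest-relationship rule the subject would be counted once, as definitely related.

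**All two-event patterns with different severities.**

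- Severity pairs: 3. Relationship combinations for each: 4 × 4 = 16. Total: 3 × 16 = 48.
- At least one event related: 3 × (16 − 2 × 2) = 36.
- Milder event related and more severe event not related, so the subject leaves the related rows: 3 × (2 × 2) = 12.
- Grade shown is weaker than the strongest grade recorded: 3 × 6 = 18.
- Related subject lost under the strongest-relationship rule: 0.

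The error runs one way in these patterns: the footnote rule can lower the related-subject count but never raise it.

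**Patterns with equal severity and different relationship grades.** There are 3 × 6 = 18, and in 3 × (2 × 2) = 12 of them one event is related and the other is not. The footnote does not say which is shown, so two programmers could report different counts.

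These are counts of logical patterns, not expected frequencies.

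**Scale of one affected subject.** SAP 3.2 plans 75 evaluable subjects in each active arm and 150 on placebo. If the safety set is about that size, one misplaced subject moves a row by 1/75 = 1.3 percentage points in an active arm and 1/150 = 0.7 on placebo.

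**Could another planned summary table supply the count?** Table 14.3.1.1 counts subjects with any related event but not by term. Table 14.3.1.2 is by term but has no relationship. Tables 14.3.1.4 to 14.3.1.6 repeat the 14.3.1.2 layout for withdrawals, serious events and deaths. None gives it.

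**The case against.** The strongest objection is that nothing is removed from the report. A reader who sees only the maximum-severity sentence might infer that a milder related event vanishes from the table. It does not: the next sentence of the same footnote keeps every event in its own row of the Events column. The subject also counts in the potentially-related line of Table 14.3.1.1, and Listing 16.2.7.1 gives each event with its rating. This stands, and it limits the point to the subject counts and percentages by term.

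A reader might also infer that Table 14.3.1.3 will fail to reconcile with Table 14.3.1.1 because of this rule. The documents do not support that. Preferred-term rows count a subject once per term, so they would not add up to the overall line under any counting rule, including the one recommended here.

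A third objection is that the footnote is silent on relationship, so a programmer could combine it with SAP 8.1 and place the subject at maximum severity and strongest relationship, each derived separately. In the example above this gives Severe / Definitely Related with Subjects 1 and Events 0, a cell that describes no event the subject had. That reading is possible, but it is not a sound way to fill the table. It does show that the footnote and SAP 8.1 need aligning.

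Finally, safety summaries are descriptive and no planned test depends on these cells. That is correct and is a reason to treat the point as minor.

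**Conclusion.** The table is wrong as written, but the defect is minor. Followed literally, the Subjects column of Table 14.3.1.3 can understate the number and percentage of subjects with a drug-related event of a given term. The correct number can be rebuilt only by counting through the listing, and the by-relationship summary that SAP 8.1 names is not delivered.

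The size is likely small. A subject is affected only by having at least two events of the same term, with the more severe one rated not or unlikely related and a milder one rated possibly or definitely related. Repeated events of one term, such as application-site reactions, will often share a causality rating, which would reduce the loss further. The documents give no rate of repeat events, no severity distribution and no proportion related, so no expected percentage loss is claimed here. The conclusion rests only on the counting rules and the table list.

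**What to change.** Replace or supplement Table 14.3.1.3 with two tables by system organ class and preferred term:

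- (a) by severity, each subject once per term at maximum severity;
- (b) by relationship, each subject once per term at strongest relationship.

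In (b), the possibly and definitely related rows then add up to the number of subjects with any related event of that term.

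Align the footnotes of both tables with SAP 8.1. If the crossed table is kept as a supplement, have its footnote say which relationship grade is shown when two events tie on severity, and refer readers to (b) for related-subject counts.

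The cost is one extra table shell. Severity and relationship are already collected for every event, so no new data are needed.
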